4.5 Risks and benefits

In a comprehensive Phase 3 program (see [Section 1.1](#)), consisting of 2 large, randomized, double-masked, multicenter studies (RTH258-C001 and RTH258-C002), treatment with brolucizumab resulted in robust visual gains and superior anatomical outcomes compared to aflibercept, with the majority of patients maintained on an Q12 dosing interval at 48 weeks, and the remainder maintained on an Q8 dosing interval. Anatomical benefits and vision gains were maintained for 2 years.

The RTH258-C001 and RTH258-C002 studies successfully evaluated a novel treatment regimen, combining the prolonged duration of effect of brolucizumab with treatment frequency guided by disease activity. Reflecting clinical practice, Investigators assessed disease activity

using both visual function and anatomical disease parameters (e.g. retinal thickness and retinal fluid). Robust clinically meaningful results were observed for both functional and anatomical outcomes in a representative nAMD population over 48 weeks and sustained up to 96 weeks.

These benefits were consistent across subgroups (e.g. age, gender, race, baseline visual acuity, baseline retinal thickness, lesion type, lesion size, and fluid status), replicated in 2 independent Phase 3 studies. Less than half of patients were identified with disease activity after the loading phase and most disease activity with adjustment of dosing interval was identified during the initial Q12 interval; the vast majority of patients without disease activity during the initial Q12 interval continued to be maintained on an Q12 treatment interval for the remainder of the treatment period indicating the benefit of early treatment monitoring in maintaining long-term efficacy. These results thus addressed the unmet medical need of delivering efficacy comparable to standard of care while reducing the treatment and monitoring burden.

The overall safety and tolerability profile of brolucizumab was consistent with aflibercept, an established therapy in patients with nAMD. While there was a higher incidence of intraocular inflammation (IOI) AEs for brolucizumab compared to aflibercept, no preferred term (PT) was reported for more than 1.5% of patients. Over 90% of IOI AEs were mild to moderate in severity and 79% resolved with no sequelae. The impact of IOI on the benefit-risk balance of brolucizumab is considered to be low.

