10.1 Definition of adverse events and reporting requirements

10.1.1 Adverse events

An AE is any untoward medical occurrence (e.g. any unfavorable and unintended sign, symptom or disease) in a patient after providing written informed consent for participation in the study. Therefore, an AE may or may not be temporally or causally associated with the use of a medicinal (investigational) product.

The Investigator has the responsibility for managing the safety of individual patient and identifying AEs.

Novartis qualified medical personnel will be readily available to advise on study-related medical questions or problems.

The occurrence of AEs must be sought by non-directive questioning of the patient at each visit during the study. AEs may also be detected when they are volunteered by the patient during or between visits or through physical examination findings, or other assessments.

AEs must be recorded in the Adverse Events eCRF under the signs, symptoms or diagnosis associated with them, accompanied by the following information (as far as possible) (if the event is serious refer to [Section 10.1.2](#)):

1. The severity grade (mild, moderate or severe as defined below)
 - mild: usually transient in nature and generally not interfering with normal activities
 - moderate: sufficiently discomforting to interfere with normal activities
 - severe: prevents normal activities
2. Its relationship to the study treatment and the ocular injection procedure. If the event is due to lack of efficacy or progression of underlying illness (i.e. progression of the study indication) the assessment of causality to study treatment will usually be 'Not suspected'. The rationale for this guidance is that the symptoms of a lack of efficacy or progression of underlying illness are not caused by the study drug, they happen in spite of its administration and/or both lack of efficacy and progression of underlying disease can only be evaluated meaningfully by an analysis of treatment arms, not on a single patient.
3. Its duration (start and end dates) or if the event is ongoing, an outcome of not recovered/not resolved must be reported.
4. Whether it constitutes a SAE (see for definition of SAE) and which seriousness criteria have been met.
5. Action taken with the study treatment. All AEs must be treated appropriately. Treatment may include one or more of the following:
 - No action taken (e.g. Further observation only)
 - Investigational treatment interrupted/withdrawn

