 - Concomitant medication or non-drug therapy given
 - Patient hospitalized/patient's hospitalization prolonged (see [Section 10.1.2](#) for definition of SAE)
6. Its outcome:
 - Not recovered/not resolved
 - Recovered/resolved
 - Recovered/resolved with sequelae
 - Fatal or unknown.
7. Its location (ocular event/non ocular event)

Conditions that were already present at the time of informed consent should be recorded in the medical history of the patient.

Adverse events (including lab abnormalities that constitute AEs) should be described using a diagnosis whenever possible, rather than individual underlying signs and symptoms.

Adverse event monitoring should be continued until 30 days (safety follow-up) after the last administration of study treatment (see “Post-treatment follow-up period” in [Section 3](#)).

Once an AE is detected, it must be followed until its resolution or until it is judged to be permanent (e.g. continuing at the end of the study), and assessment must be made at each visit (or more frequently, if necessary) of any changes in severity, the suspected relationship to the interventions required to treat it, and the outcome.

Information about adverse drug reactions for the investigational drug can be found in the IB.

Abnormal test results constitute AEs only if they fulfill at least one of the following criteria:

- they induce clinical signs or symptoms
- they are considered clinically significant
- they require therapy

Clinically significant abnormal test results must be identified through a review of values outside of normal ranges/clinically notable ranges, significant changes from Screening/Baseline or the previous visit, or values which are considered to be non-typical in patients with the underlying disease. Investigators have the responsibility for managing the safety of individual patients and identifying AEs.

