2.9 Safety analyses

Safety measurements include duration of exposure, vital signs, and adverse events (AEs). All safety endpoints will be summarized using the Safety Set. Patients will be analyzed according to the treatment received. No imputation will be carried out for missing data.

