- More than one occurrence will be counted if there is > 1 day gap between the end date of the preceding AE and the start date of the consecutive AE.

For occurrence, the presence of at least one SAE / SAE suspected to be related to study treatment / non SAE has to be checked in a block e.g., among AE's in a ≤ 1 day gap block, if at least one SAE is occurring, then one occurrence is calculated for that SAE.

The number of deaths resulting from SAEs suspected to be related to study treatment, procedure and SAEs irrespective of study treatment relationship will be provided by SOC and PT.

In addition, all treatment emergent AEs and SAE will also be listed.

The by-patients listing will include: SOC/PT/Verbatim term, start date, end date, severity, USM, relationship to study treatment and procedures, whether or not it is a SAE, action taken with study treatment and outcome; duration will be calculated as (end date – start date + 1) and for ongoing AE (last visit date – start date + 1) by ocular and non-ocular. For ocular then it will be presented by study eye, fellow eye and any eye.

A summary of action taken with number and percentage of patients will presented with treatment interrupted, treatment withdrawn, not applicable and unknown.

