2.9.1.1 Adverse events of special interest / grouping of AEs

The number (%) of patients with adverse events of special interest (AESI) will be summarized by Standardized MedDRA Query and PT. A listing will also be provided.

A Case Retrieval Sheet (CRS) with the exact composition of the AE groupings is to be used to map reported AEs to the AESI groupings. This file may be updated (i.e. it is a living document) based on review of accumulating trial data, and therefore the groupings are also subject to potential change. The most up-to-date version of the CRS will be used at the time of the analysis.

The number and percentage of patients with any AESI, having an AESI in each SOC and having each individual AE (PT) will be presented by SOC and PT.

The number and percentage of patients by AESI type along with incidence rate per patient and per 1000 injections will be provided. Incidence rate per patient is defined as number of patients in AESI type/total number of patients in safety analysis set and incidence rate per 1000 injection is define as (number of occurrence of AESI type/total number of injections)*1000.

The number and type of AESI will be plotted according to the time after last brolucizumab injection and time since first brolucizumab injection.

Summary statistics for change from baseline in BCVA after end date of AESI will be provided for each AESI type and change from baseline in BCVA will be plotted overall and for each type of AESI.

Patients demographics, baseline characteristics and medical history will be provided for AESI patient with safety set.

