5.1.2 AE date imputation

AE date imputation is based only on a comparison of the partial AE start date to the treatment start date as mentioned in the below.

1. If the AE start date year value is missing, the date uncertainty is too high to impute a rational date. Therefore, if the AE year value is missing, the imputed AE start date is set to NULL.
2. If the AE start date year value is less than the treatment start date year value, the AE started before treatment. Therefore:
 - a. If the AE year is less than the treatment year and the AE month is missing, the imputed AE start date is set to the mid-year point (01JulYYYY).
 - b. Else if the AE year is less than the treatment year and the AE month is not missing, the imputed AE start date is set to the mid-month point (15MONYYYY).

3. If the AE start date year value is greater than the treatment start date year value, the AE started after treatment. Therefore:
 - a. If the AE year is greater than the treatment year and the AE month is missing, the imputed AE start date is set to the year start point (01JanYYYY).
 - b. Else if the AE year is greater than the treatment year and the AE month is not missing, the imputed AE start date is set to the month start point (01MONYYYY).
4. If the AE start date year value is equal to the treatment start date year value:
 - a. And the AE month is missing or the AE month is equal to the treatment start month, the imputed AE start date is set to one day after treatment start.
 - b. Else if the AE month is less than the treatment start month, the imputed AE start date is set to the mid-month point (15MONYYYY).
 - c. Else if the AE month is greater than the treatment start month, the imputed AE start date is set to the start month point (01MONYYYY).

	MON		MON < CFM		MON = CFM		MON > CFM					
	MISSING											
YYYY MISSING	NULL		NULL		NULL		NULL					
	Uncertain		Uncertain		Uncertain		Uncertain					
YYYY < CFY	(D) = 01JULYYYY		(C)= 15MONYYYY		(C)= 15MONYYYY		(C)= 15MONYYYY					
	Before Treatment Start		Before Treatment Start		Before Treatment Start		Before Treatment Start					
YYYY = CFY	(B)= TRTSTD+1		(C)= 15MONYYYY		(A)= TRTSTD+1		(A)= 01MONYYYY					
	Uncertain		Before Treatment Start		Uncertain		After Treatment Start					
YYYY > CFY	(E)= 01JANYYYYY		(A)= 01MONYYYY		(A)= 01MONYYYY		(A)= 01MONYYYY					
	After Treatment Start		After Treatment Start		After Treatment Start		After Treatment Start					

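### The AESI vision statistics use only BCVA after the event has ended, so unresolved events contribute nothing and the table is conditional on recovery

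*SAP*

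**What the plan says.** SAP 2.9.1.1 plans this: "Summary statistics for change from baseline in BCVA after end date of AESI will be provided for each AESI type". The same sentence goes on to a graph: "change from baseline in BCVA will be plotted overall and for each type of AESI". No time anchor is given for the graph. Interim SAP 2.10.1.1 repeats both parts.

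Protocol 10.1.1 governs the event record. An AE is followed until it resolves or "until it is judged to be permanent (e.g. continuing at the end of the study", and "if the event is ongoing, an outcome of not recovered/not resolved must be reported". Resolved with sequelae is a separate outcome category.

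Three SAP rules could bear on an event without an end date:

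- SAP 2.9, on missing safety data: "No imputation will be carried out for missing data".
- SAP 5.1.2, on AE dates: "AE date imputation is based only on a comparison of the partial AE start date to the treatment start date". It has no rule for end dates.
- SAP 2.9.1, on the duration shown in the by-patient AE listing: "for ongoing AE (last visit date – start date + 1".

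Protocol 9.1.1 and Table 8-1 ask for BCVA to be collected to at least Week 48 after study treatment is stopped early.

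**The concern.** Protocol 1.1 and 4.5 warn that intraocular inflammation (IOI), retinal vasculitis and retinal vascular occlusion can lead to severe vision loss, and these events drove several amendments. A reader of the study report will look to the AESI vision table to see what they did to sight. Having an end date is itself an outcome of the event. Requiring one selects patients on recovery, and patients whose event has not resolved leave the calculation without any statement that they have left. The table also gives no figure for vision during the event.

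**Working it through.** **Step 1: apply the written rule to each outcome.**

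| Outcome (Protocol 10.1.1) | End date? | BCVA after end date possible? | In the table? |
|---|---|---|---|
| Resolved | Yes | Yes | Yes |
| Resolved with sequelae | Can have one | Yes | Yes, if dated |
| Not resolved / ongoing | No | No | No |

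No other rule changes the last row. SAP 5.1.2 handles start dates only. SAP 2.9 rules out imputation. The last-visit rule in SAP 2.9.1 serves the listed duration; if it were borrowed as an end date, no BCVA would lie after it and the event would still contribute nothing.

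**Step 2: size of the gap.** The plan gives no figure here to reproduce. Let f be the share of AESI patients whose event is unresolved, and R and U the mean BCVA change from baseline in resolved and unresolved events.

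- Mean over all AESI patients = (1 − f) × R + f × U
- Planned table = R
- Gap = R − [(1 − f) × R + f × U] = f × (R − U)

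The documents give none of f, R or U, so all values below are assumptions. Gap in letters:

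| f | R = 0, U = −5 | R = 0, U = −15 | R = 0, U = −30 | R = −2, U = −15 |
|---|---|---|---|---|
| 5% | 0.25 | 0.75 | 1.5 | 0.65 |
| 10% | 0.5 | 1.5 | 3.0 | 1.3 |
| 21% | 1.05 | 3.15 | 6.3 | 2.73 |
| 30% | 1.5 | 4.5 | 9.0 | 3.9 |

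For example, f = 30% and U = −30 give 0.30 × 30 = 9.0; f = 5% and U = −5 give 0.05 × 5 = 0.25. If U = R the gap is zero.

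The 21% row is an upper-end illustration. Protocol 4.5 says of the earlier Phase 3 programme: "Over 90% of IOI AEs were mild to moderate in severity and 79% resolved with no sequelae". The remaining 100 − 79 = 21% mixes unresolved events with events resolved with sequelae, and it counts events, not patients.

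**Step 3: how many patients.** Protocol 4.5 gives IOI-related AE rates of 3.2% in men and 5.3% in women in the two pivotal trials. With 295 patients:

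- 295 × 0.032 = 9.4 and 295 × 0.053 = 15.6 patients with IOI
- 9.4 × 0.21 = 2.0 and 15.6 × 0.21 = 3.3 unresolved, as an upper end

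The 9.3% in Protocol 4.2 comes from a trial of continued 4-weekly dosing, which this protocol does not allow after loading. It would give 295 × 0.093 = 27.4 patients, but it is not a rate for this regimen. With about 9 to 16 cases, the loss of two or three could move a mean noticeably.

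**The case against.** The SAP does not say that unresolved events are excluded, and table details are left to shells and programming specifications that are not part of these documents. That is true. Still, the end-date condition is explicit, and a programmer who follows it has no qualifying value for an ongoing event. This is more than missing detail.

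Four stronger readings are tempting, and the documents do not support them:

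- *This is the only planned look at visual harm.* It is the only set of AESI-specific BCVA summary statistics. The plots carry no end-date condition and may include unresolved events. The incidence tables count every on-treatment AESI, and the by-patient listing in SAP 2.9.1 shows outcome. These are weaker substitutes for a vision summary. The by-visit BCVA table in SAP 2.7.1.4 is not split by AESI, and under SAP 2.2 it leaves out unscheduled visits.
- *The events with lasting vision loss are the ones lost.* An inflammation that ends but leaves reduced acuity can be recorded as resolved with sequelae, carry an end date and stay in the table. An open event may be mild or recent.
- *The harm is understated.* The direction depends on unresolved eyes seeing worse than resolved ones. That is plausible, but no section links unresolved status to BCVA.
- *The bias is larger at the interim.* More events may be open at a cut-off simply because they began recently. The documents do not settle this.

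It is also fair to say that the stakes are limited. The table is descriptive, in a single-arm study, and no decision rule is tied to it.

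**Conclusion.** The point holds as a selection problem in one safety table, repeated in the interim SAP. Following the text, AESIs that are ongoing or not resolved contribute no BCVA, so the result describes recovered events only. The size is f × (R − U): 0.25 to 9.0 letters for f of 5% to 30%, R = 0 and U of −5 to −30. That range rests wholly on assumed values, and its sign rests on U being lower than R. I hold the selection with high confidence and the direction with moderate confidence. The primary endpoint and the secondary endpoints, including AE incidence, are untouched. It should be fixed before the final report, but it does not threaten the study's main conclusion.

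**What to change.** In SAP 2.9.1.1:

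1. Summarise change from baseline in study-eye BCVA for every Safety Set patient with a study-eye AESI, by AESI type, using values from AESI onset onward.
2. Use the last available BCVA up to Week 48/50. State that unscheduled and post-discontinuation values count, so that the censoring rule in Protocol 12.4.3 (written for the primary endpoint) is not carried over.
3. As a supplement, report the lowest BCVA after onset.
4. Split by outcome (resolved, resolved with sequelae, not resolved) and show the number unresolved.
5. Keep the post-end-date summary as secondary.
6. Qualify any interim AESI vision table already produced under the same rule. The final SAP describes the interim analysis as already performed.

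The cost is SAP wording and slightly more programming. No new data are needed where the planned BCVA was obtained, although Protocol 9.1.1 also allows follow-up by telephone or email, so some late values may be absent. Two downsides need footnotes: the last value may follow a switch to standard-of-care anti-VEGF, and the lowest value tends to fall as the number of measurements rises, even without true loss. With few cases, the outcome split will be sparse and should be read alongside the individual listings.

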2.9.2 Deaths

A separate summary of deaths including on-treatment and post-treatment deaths will be provided.

All deaths in the clinical database will be listed with the investigator-reported principal cause. Deaths occurring after the first dose of study treatment until 30 days after the date of last

treatment will be summarized. In addition, deaths occurring after the first dose of study treatment until the date of last treatment will also be summarized.

2.9.3 Laboratory data

Not applicable

2.9.4 Other safety data

Not applicable

2.9.4.1 ECG and cardiac imaging data

Not applicable

2.9.4.2 Vital signs

Vital signs will include blood pressure and pulse rate measurements.

All vital signs data will be listed by patient, and visit, and if ranges are available, abnormalities will be flagged. Abnormal values are marked in [Section 5.3](#). All data, including data from unscheduled visits, will be considered when identifying abnormal values. Analysis of vital sign measurements using summary statistics for the change from Baseline for each post-baseline visit will be performed. These descriptive summaries will be presented by vital sign. Change from Baseline will only be summarized for patients with both Baseline and post-baseline values.

2.10 Pharmacokinetic endpoints

Not applicable

2.11 PD and PK/PD analyses

Not applicable

[REDACTED]

[REDACTED]

[REDACTED]

[REDACTED]

[REDACTED]

[REDACTED]

[REDACTED]

[REDACTED]

2.13 Biomarkers

Not applicable

2.14 Other Exploratory analyses

Not applicable

2.15 Interim analysis

An interim analysis was performed when the last patient included completed the Week-16 visit. Patients remained in the study and continued to receive treatment through the maximum planned duration of treatment of 44/46 weeks to allow for further evaluation of efficacy and safety.

3 Sample size calculation

The sample size calculation is based on the hypothesis of 25% to 35% of patients with no disease activity at Week 16. The sample size analyses were performed before the USM were introduced.

Table 3-1 Confidence intervals for proportions (2 sided)

Confidence level	Sample size (N)	Expected proportion	Target distance from proportion to limit
0.950	250	0.25	0.054
0.950	300	0.25	0.049
0.950	325	0.25	0.047
0.950	400	0.25	0.042
0.950	250	0.30	0.057
0.950	300	0.30	0.052
0.950	325	0.30	0.050
0.950	400	0.30	0.045
0.950	250	0.35	0.059
0.950	300	0.35	0.054
0.950	325	0.35	0.052
0.950	400	0.35	0.047

A sample size of 250 to 400 patients produces a 2-sided 95% confidence interval with a distance from the proportion to the limits ranges from 0.042 to 0.059 when the estimated proportion varies from 0.25 to 0.35 (nQuery Advisor version 7.0).

In the HAWK and HARRIER studies, the proportion of naïve nAMD patients treated with brolucizumab who had disease activity at Week 16 was 30% less than for patients treated by aflibercept.

To determine a similar 30% proportion of patients with no disease activity at Week 16 in this pretreated study with a precision of 5% and alpha 5% (2-sided 95% confidence interval of width 11%), a total of 265 patients have to be observed in this study.

Slow recruitment rate was observed in conduct phase of study due to COVID-19, therefore, the sample size was adjusted. The adjusted sample size was significant enough to provide 95% confidence interval.

Considering a dropout rate of 10%, a total of 295 patients will be included.

4 Change to protocol specified analyses

Not applicable

5 Appendix

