12.8 Sample size calculation

The sample size calculation is based on the hypothesis of 25% to 35% of patients with no disease activity at Week 16. The sample size analyses were performed before the urgent safety measures were introduced.

Table 12-1 Confidence intervals for proportions (2 sided)

Confidence level	Sample size (N)	Expected proportion	Target distance from proportion to limit
0.950	250	0.25	0.054
0.950	300	0.25	0.049
0.950	325	0.25	0.047
0.950	400	0.25	0.042
0.950	250	0.30	0.057
0.950	265	0.30	0.055
0.950	300	0.30	0.052
0.950	325	0.30	0.050
0.950	400	0.30	0.045
0.950	250	0.35	0.059
0.950	300	0.35	0.054
0.950	325	0.35	0.052
0.950	400	0.35	0.047

A sample size of 250 to 400 patients produces a 2-sided 95% confidence interval with a distance from the proportion to the limits ranges from 0.042 to 0.059 when the estimated proportion varies from 0.25 to 0.35 (nQuery Advisor version 7.0).

In the HAWK and HARRIER studies, the proportion of naïve nAMD patients treated with brolucizumab who had disease activity at Week 16 was 30% less than for patients treated by aflibercept.

To determine a similar 30% proportion of patients with no disease activity at Week 16 in this pretreated study with a precision of 5.5% and alpha 5% (2-sided 95% confidence interval of width 11%), a total of 265 patients have to be observed in this study.

Considering a dropout rate of 10%, a total of 295 patients will be included.

13 Ethical considerations and administrative procedures

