5.3	Laboratory parameters derivations	35
5.4	Statistical models	35
5.5	Rule of exclusion criteria of analysis sets	36
6	Reference	38

List of abbreviations

AE	Adverse event
ATC	Anatomical Therapeutic Classification
BCVA	Best-Corrected Visual Acuity
CNV	Choroidal Neovascularization
CI	Confidence Interval
CRO	Contract Research Organization
CSFT	Central Sub-Field Retinal Thickness
CRT	Central Retinal Thickness
CSR	Clinical Study report
ENR	Enrolled set
FAS	Full Analysis Set
ECS	Edit checks specification
eCRF	Electronic Case Report Form
ICF	Informed Consent Form
IVT	Intravitreal
KM	Kaplan-Meier
MedDRA	Medical Dictionary for Drug Regulatory Affairs
nAMD	Neovascular Age-Related Macular Degeneration
OCT	Optical Coherence Tomography
PK	Pharmacokinetics
PD	Protocol deviation
PDS	Programming Datasets Specifications
PPS	Per-Protocol Set
PT	Preferred Term
q12w	Every 12 Weeks
SAP	Statistical Analysis Plan
SAF	Safety analysis set
SD-OCT	Spectral Domain Optical Coherence Tomography
SOC	System Organ Class
TFL	Tables, Figures, Listings
TtC	Treat-to-Control
USM	Urgent Safety Measure
WHO	World Health Organization

1 Introduction

The purpose of this Statistical Analysis Plan (SAP) is to describe the implementation of the statistical methods for all safety and efficacy analyses planned (Protocol-Section 12) in the clinical protocol (CRTH258AFR03, version no: 05, release date 05Apr2022). This document will be used to prepare the statistical results and the corresponding Clinical Study Report (CSR).

The details of CSR deliverables (shells for tables, figures and listings) and further programming specifications will be described in the Tables, Figures & Listings (TFL) shells and Programming Datasets Specifications (PDS) respectively, which will be included in this document.

Data will be analyzed by Novartis and/or the designated Contract Research Organization (CRO). Statistical software SAS version 9.4 or higher will be used for generating TFLs.

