2.6 Analysis of the primary objective

2.6.1 Primary endpoint

The primary objective of this study is to evaluate the effect of brolucizumab 6 mg on disease control. The primary efficacy endpoint is the proportion of patients with no disease activity at Week 16 in the study eye.

Estimation for the proportion of disease control involves only calculating the ratio of successes. In this study

Event: 1= no disease activity (disease control)

0= disease activity (failure)

Count: Frequency or number of patients with no disease activity (disease control) at Week 16.

Proportion: Number of patients with no disease activity (disease control) at Week 16/Total number of patients in the FAS.

The number of disease control patients at Week 16, total number of evaluable patients, percentage of disease control and 95% confidence interval (CI) using the Clopper-Pearson method will be provided.

Sensitivity analysis will be performed for primary endpoint using last observation carried forward (LOCF) method and considering disease activity for missing data at Week 16.

A sensitivity analysis in patients exposed and not-exposed to USM will be performed for below estimand.

- a) Proportion of patients with no disease activity at Week 16.
- b) Status of patients with disease activity before and after introduce of USM.

The above analysis will be done on the FAS and only on the study eye.

The analysis will be performed on the PPS, if there is more than a 10% difference in patients, between FAS and the PPS.

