COMD01	Prohibited medication/procedures	Included in everything	0
COMD02	Non-permitted steroid use	Included in everything	0
TRT01	Trt > 3 days after inj visit	Included in everything	0
TRT02	Missed injection visit	Included in everything	0
TRT03	Wrong IP/volume administered	Included in everything	2
TRT04	IVT interval<than 21 days	Included in everything	0
TRT05	TRT admin prior effic/safty eval	Included in everything	0
TRT06	COVID-19 Drug supply change	Included in everything	0
TRT07	COVID-19 Treatment not given	Included in everything	0
TRT08	Missed Injection loading phase	Excluded from FAS and PPS	1
TRT09	Missed Injection	Included in everything	0
TRT10	No Disease acty bt INJ is given	Included in everything	0
TRT11	Treatment given at EOS	Included in everything	0
TRT12	anti-VEGF therapy during tria	Included in everything	0
WITH01	Withdrew constn nt discontinued	Excluded from FAS and PPS	1
OTHER01	Missed mandatory visit	Excluded from PPS	2
OTHER02	Subject rescreened > once	Excluded from PPS analysis	0
OTHER03	New ICF is missing-rescreened	Excluded from FAS and PPS	1
OTHER04	Rescrn >14days w/o scr proc	Included in everything	0
OTHER05	Odysight used w/o consent	Included in everything	0
OTHER06	Temp excursion IP administered	Included in everything	0
OTHER07	SAE not reported	Included in everything	0
OTHER08	Crit met to failure	Included in everything	0
OTHER09	The patient done rescreening	Included in everything	0
OTHER10	COVID-19 Missed visit	Included in everything	0
OTHER11	COVID-19 Visit not at site	Included in everything	0
OTHER12	COVID-19 Assessment changed	Included in everything	0

Deviation ID	Description of Deviation	Exclusion in Analyses	Severity code
OTHER13	COVID-19 Discontinuation	Included in everything	0
OTHER14	Visit window > 7 days	Included in everything	0
OTHER15	Efficacy assessment not done	Excluded from PPS	2
OTHER16	Safety assessment not done	Included in everything	0
OTHER17	BCVA not done correctly	Included in everything	0
OTHER18	Trt regimen wrongly adjusted	Included in everything	0
OTHER19	Vital signs/safety call not done	Included in everything	0
OTHER20	Imaging analyzed after WoC	Included in everything	0

Table 5-2 Patient Classification

Analysis Set	Severity codes that cause a subject to be excluded
ENR	NA
FAS	1
PPS	1, 2
SAF	NA

6 Reference

[HAWK] ClinicalTrials.gov. Identifier NCT02307682. Available at <https://clinicaltrials.gov/ct2/show/NCT02307682> (link is external). Accessed November 2017.

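### Both SAPs state 5% precision for 265 patients; the 11% interval width in the same sentence, and the protocol, give 5.5%

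*SAP*

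**What the plan says.** The final SAP, section 3, bases the sample size on an expected 30% of patients without disease activity at Week 16, "with a precision of 5% and alpha 5% (2-sided 95% confidence interval of width 11%), a total of 265 patients". The interim-analysis SAP (IA-SAP), section 3, has the same wording. Both then allow for 10% dropout and arrive at 295.

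Protocol 12.8 has the same sentence "with a precision of 5.5% and alpha 5"%, with the same 11% width, the same 265 and the same 295. Protocol Table 12-1 includes the row 265 / 0.30 / 0.055. Table 3-1 in each SAP omits that row. In all three tables the underlined row is 325 / 0.30 / 0.050.

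Each SAP states in its introduction that it implements the methods planned "in the clinical protocol (CRTH258AFR03, version no: 05, release date 05Apr2022"), and each reports no departures in its section 4 on changes to protocol-specified analyses.

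The final SAP alone adds, about the reduced sample size: "The adjusted sample size was significant enough to provide 95% confidence interval".

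**The concern.** The last column of the tables defines precision as the distance from the estimate to a confidence limit. On that definition a precision of 5% is an interval 10% wide, so each SAP gives two incompatible precisions in one sentence. The 5% also disagrees with the protocol version that both SAPs cite, so an older protocol does not explain it. Nor is it recorded as an intended change.

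The primary analysis is one proportion with a 95% confidence interval (protocol 12.4.2; SAP 2.6.1). No hypothesis is tested and there is no power calculation, so the expected precision is the only stated reason for the number of patients. The SAP is the source for the clinical study report, and a figure that overstates the planned precision could be carried into it.

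The final SAP's remark on the adjusted sample size does not help. Any sample size yields a 95% confidence interval; what matters is how wide it is.

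**Working it through.** **Inputs.** Expected proportion p = 0.30 and two-sided 95% confidence (all three documents). n = 265 observed, 10% dropout, 295 included (all three). Stated precision 5% (both SAPs) or 5.5% (protocol). Stated width 11% (all three).

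**1. Reproduce the tables.** Half-width d = 1.96 × √(p(1 − p)/n).

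| n | p | computed | table |
|---|---|---|---|
| 250 | 0.25 | 0.0537 | 0.054 |
| 250 | 0.30 | 0.0568 | 0.057 |
| 300 | 0.30 | 0.0519 | 0.052 |
| 325 | 0.30 | 0.0498 | 0.050 |
| 400 | 0.35 | 0.0467 | 0.047 |

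All 13 rows of protocol Table 12-1, and so all 12 rows of Table 3-1 in the SAPs, match to three decimals. The normal approximation is therefore the documents' own method.

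**2. Precision at n = 265.** 1.96 × √(0.30 × 0.70/265) = 0.0552. Width = 2 × 0.0552 = 0.110. This agrees with the 11% in the sentence and with the protocol's 5.5%.

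**3. Sample size for each stated precision.** n = 1.96² × 0.21/d².
- d = 0.05: 322.7, so 323 observed.
- d = 0.055: 266.7, so 267, within two patients of 265.

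**4. Check from the SAPs' own table.** At p = 0.30, Table 3-1 gives 0.057 for 250 and 0.052 for 300. The value for 265 must lie between these, above 0.050.

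**5. Could another method give 5% at 265?** No. The Wilson half-width is 0.0549. With a continuity correction, 5 points would need 343 patients.

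**6. Could the 5% refer to all 295 included?** No. 1.96 × √(0.21/295) = 0.0523. That is also a best case, because SAP Table 5-1 removes patients from the full analysis set for some deviations, for example "Missed Injection loading phase".

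**7. Dropout.** 265/0.90 = 294.4, rounded up to 295, as stated.

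**8. The interval that will be reported.** SAP 2.6.1 plans "percentage of disease control and 95% confidence interval (CI) using the Clopper-Pearson method". The lower limit is the 2.5% quantile of Beta(x, n − x + 1) and the upper limit is the 97.5% quantile of Beta(x + 1, n − x). With n = 265 and x = 0.30 × 265, the limits lie 5.45 points below and 5.91 points above the estimate, width 11.4%. As an integer check, 80/265 gives 24.7% to 36.1%, also 11.4% wide. The planned interval is thus slightly wider than the 11% from the normal approximation.

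**The case against.** The strongest reply is that this is a one-figure slip in a descriptive section. The 265, the 295, the dropout allowance and the 11% width are all right in the same place, the governing protocol is right, and the interim analysis has already been run. No estimate, analysis set or method depends on the figure. All of that stands, and it is why the correction is small. It does not make the sentence correct, and the sentence states the only justification for the sample size.

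It can also be said that the remark on the adjusted sample size directly follows the sentence on precision, so context supplies what it lacks. That is partly fair: once 5% becomes 5.5%, the precision is stated. The remark still offers as a justification something that is true of any sample size.

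The 5% matches the underlined 325 / 0.050 row, so it may be left over from a larger target. That is an inference; no document says what the underline means.

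Three stronger readings are tempting, and the documents do not support them.
- **The trial is too small and needs 323 observed patients (359 with dropout, 323/0.90 = 358.9).** The protocol's target is 5.5%, and its Amendment 5 reduced the sample size deliberately, judging the precision acceptable.
- **The 30% was wrongly derived.** The pivotal result cited beside it is a comparison, patients "who had disease activity at Week 16 was 30% less than for patients treated by aflibercept", so a reader might call 30% a misreading. But protocol 12.8 presents 25% to 35% as a hypothesis. Any back-calculation must take rounded figures as exact and relative, and the pivotal patients were treatment-naive whereas these are pretreated. It would not change the sample size.
- **The SAS code would produce the wrong interval.** The code in the appendices is a generic template not assigned to the primary endpoint, and the text names Clopper-Pearson.

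**Conclusion.** The concern holds as an error of statement. For 265 patients at 30%, the precision is 5.5 points (width 11.0%), not 5. Both SAPs understate the half-width by about half a point and contradict their own sentence, their own table and the protocol they implement. The result rests on the 30% planning value and on the normal approximation, which is shown to be the method behind the tables; none of the other interval methods tried gives 5 points at 265.

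The sample size, the planned analysis and the conclusions drawn from the data are unaffected. The correction should be made because precision is the sole rationale for the number of patients.

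**What to change.** Keep 265 observed and 295 included.

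- **Final SAP, section 3.** Change the stated precision from 5% to 5.5% (normal approximation). Add the row 265 / 0.30 / 0.055 to Table 3-1 and highlight it in place of 325 / 0.050.
- **Final SAP, section 3.** Replace the sentence on the adjusted sample size with one labelled by method, for example: *At an assumed 30%, the planned Clopper-Pearson interval with 265 evaluable patients has limits about 5.5 points below and 5.9 points above the estimate (width 11.4%), slightly wider than the 11% normal-approximation width.* Labelling both figures prevents 11% and 11.4% from looking like a new contradiction.
- **IA-SAP, section 3.** Make the same correction to the figure and table, or record it in a note to file, because the final SAP (2.15) reports that "An interim analysis was performed when the last patient included completed the Week-16 visit".
- **Protocol.** No change. Its figure is already correct, and section 14.1 requires a formally approved amendment for any edit.

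The cost is one figure, one table row with its highlighting and one sentence in the final SAP, and one figure and one row, or a note, for the IA-SAP. No patients are added and nothing is reanalysed.
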